12.7 Safety objectives

12.7.1 Analysis set and grouping for the analyses

For all safety analyses, the safety set will be used. All listings and tables will be presented by treatment received.

The overall observation period will be divided into three mutually exclusive segments:

1. pre-treatment period: from day of patient's informed consent to the day before first dose of study medication
2. on-treatment period: from day of first dose of study medication to x days after last dose of study medication

12.7.2 Adverse events (AEs)

All information obtained on adverse events will be displayed by treatment and participant.

Summary tables for adverse events (AEs) will include only AEs that started or worsened during the on-treatment period. The number (and percentage) of participants with treatment emergent AEs will be summarized by primary system organ class, preferred term and maximum severity (based on CTCAE grades). Separate summaries will be provided for study medication related adverse events, deaths, serious adverse events, adverse events leading to treatment discontinuation, and adverse events leading to dose adjustment. The number (and percentage) of participants with adverse events will be summarized by primary system organ class, preferred term and maximum severity.

Separate summaries will be provided for study medication related adverse events, death, serious adverse events, adverse events leading to treatment discontinuation, and adverse events leading to dose adjustment.

The incidence of adverse events will be summarized by system organ class and or preferred term, severity (based on CTCAE grades), type of adverse event, relation to study treatment.

Serious adverse events and non-serious adverse events will be tabulated.

Selected summaries of adverse events will be produced for the overall safety period. All deaths (on-treatment and post-treatment) will be summarized.

All AEs, deaths, and serious adverse events (including those from the pre- and post-treatment periods) will be listed and those collected during the pre-treatment, post-treatment and overall safety period will be flagged.

12.7.3 Laboratory abnormalities

Grading of laboratory values will be assigned programmatically as per NCI CTCAE version 5.0. The calculation of CTCAE grades will be based on the observed laboratory values only, clinical assessments will not be taken into account.

CTCAE Grade 0 will be assigned for all non-missing values not graded as 1 or higher. Grade 5 will not be used.

For laboratory tests where grades are not defined by CTCAE v5, results will be categorized as low/normal/high (or other project-specific ranges, if more suitable) based on laboratory normal ranges.

The following summaries will be generated separately for hematology and biochemistry tests: For laboratory tests where grades are defined by CTCAE v5

- Worst post-baseline CTCAE grade (regardless of the baseline status). Each patient will be counted only once for the worst grade observed post-baseline.
- Shift tables to compare baseline CTCAE grades to the worst on-treatment grade For laboratory tests where grades are not defined by CTCAE v5
- Shift tables using the low/normal/high/(low and high) (or project specific) classification to compare baseline to the worst on-treatment value.

Listing of all laboratory data with values flagged to show the corresponding CTCAE v5 grades if applicable and the classifications relative to the laboratory normal ranges will be presented.

12.7.4 Other safety data

ECG

A 12-lead ECG including PR, QRS, QT, QTcF, QTcB and RR intervals will be obtained for each patient during the study. ECG data will be read and interpreted centrally.

Absolute values/change from baseline will be summarized over time. As appropriate, the number and percent of patients will be tabulated by category. In addition, a listing of patients with at least one notable ECG value will be produced.

Vital signs

Data on vital signs will be tabulated and summarized descriptively as follows:

- Number and frequency of patients who shift from non-notable at baseline to notable post- baseline (details about the definition of notable abnormal results will be given in the SAP)
- All information collected will be listed and notable values will be flagged.

[REDACTED]

[REDACTED]

[REDACTED]

12.8 Interim analysis

As the primary time point is by 24 weeks, the primary analysis will be an interim analysis. The primary analysis will be performed when the last patient completes 24 weeks of treatment or discontinues early.

As appropriate, annual interim analyses will be planned for publication or any regulatory purpose. No formal interim analysis will be performed. Only summary statistics will be provided.

Final Analysis will be performed when the last patient completes 72 weeks or discontinues early. A final CSR will be written.

12.9 Sample size calculation

This is an open label, three-cohort study to assess safety and efficacy of study of asciminib (ABL001) monotherapy in patients with chronic myeloid leukemia in chronic phase (CML-CP) previously treated with at least 2 prior TKIs (tyrosine kinase inhibitors) and CML-CP patients harboring the T315I mutation previously treated with at least 1 prior TKIs

For all CML-CP with the exception of those harboring the T315I mutation, there will be randomization to eliminate selection bias at the time of cohort allocation. Those patients will be assigned to either Cohort A consisting of asciminib 40 mg BID patients or Cohort B consisting of asciminib 80 mg QD. For CML-CP patients harboring the T315I mutation, they will be assigned to Cohort C with asciminib 200 mg BID, which is the dose required for that patient population. It is worthwhile mentioning that randomization for cohorts A and B will be

pursued for patient selection only. The study is not powered to show differences in Primary and Secondary endpoints between study cohorts.

Primary objective of the study is to assess safety profile of this combination drug during 24 weeks for all cohort patients.

A sample size of 40 evaluable patients for Cohort A is estimated based on a two- sided 95% confidence interval for an incidence rate of an AE using the large sample normal approximation that will extend 0.12 from the observed incidence rate of an AE (precision or margin of error of 12%) for an expected incidence rate of 18%. Considering drop-out rate of 10%, approximately 45 patients will be enrolled for safety assessment for the Cohort A of this study.

Retaining the same assumptions, approximately 45 patients will also be enrolled for Cohort B. Additionally for Cohort C, approximately 25 patients will be enrolled.

Thus, approximately total 115 (45+45+25=115) patients will be enrolled for Cohort A (n1=45) and Cohort B (n2=45) and for Cohort C (n3=25) of the study.

13 Ethical considerations and administrative procedures

13.1 Regulatory and ethical compliance

This clinical study was designed and shall be implemented, executed and reported in accordance with the ICH Harmonized Tripartite Guidelines for Good Clinical Practice, with applicable local regulations (including European Directive 2001/20/EC, US CFR 21), and with the ethical principles laid down in the Declaration of Helsinki.

13.2 Responsibilities of the investigator and IRB/IEC

Before initiating a trial, the investigator/institution must obtain approval/favorable opinion from the Institutional Review Board/Independent Ethics Committee (IRB/IEC) for the trial protocol, written informed consent form, consent form updates, participant recruitment procedures (e.g., advertisements) and any other written information to be provided to participants. Prior to study start, the investigator is required to sign a protocol signature page confirming his/her agreement to conduct the study in accordance with these documents and all of the instructions and procedures found in this protocol and to give access to all relevant data and records to Novartis monitors, auditors, Novartis Quality Assurance representatives, designated agents of Novartis, IRBs/IECs, and regulatory authorities as required. If an inspection of the clinical site is requested by a regulatory authority, the investigator must inform Novartis immediately that this request has been made.

13.3 Publication of study protocol and results

The protocol will be registered in a publicly accessible database such as clinicaltrials.gov and as required in EudraCT. In addition, after study completion (defined as last patient last visit) and finalization of the study report the results of this trial will be submitted for publication and posted in a publicly accessible database of clinical trial results, such as the Novartis clinical trial results website and all required Health Authority websites (e.g. Clinicaltrials.gov, EudraCT etc.).

For details on the Novartis publication policy including authorship criteria, please refer to the Novartis publication policy training materials that were provided to you at the trial investigator meetings.

13.4 Quality Control and Quality Assurance

Novartis maintains a robust Quality Management System (QMS) that includes all activities involved in quality assurance and quality control, to ensure compliance with written Standard Operating Procedures as well as applicable global/local GCP regulations and ICH Guidelines.

Audits of investigator sites, vendors, and Novartis systems are performed by auditors, independent from those involved in conducting, monitoring or performing quality control of the clinical trial. The clinical audit process uses a knowledge/risk based approach.

Audits are conducted to assess GCP compliance with global and local regulatory requirements, protocols and internal SOPs, and are performed according to written Novartis processes.

14 Protocol adherence

This protocol defines the study objectives, the study procedures and the data to be collected on study participants. Additional assessments required to ensure safety of participants should be administered as deemed necessary on a case by case basis. Under no circumstances including incidental collection is an investigator allowed to collect additional data or conduct any additional procedures for any purpose involving any investigational drugs under the protocol, other than the purpose of the study. If despite this interdiction prohibition, data, information, observation would be incidentally collected, the investigator shall immediately disclose it to Novartis and not use it for any purpose other than the study, except for the appropriate monitoring on study participants.

Investigators ascertain they will apply due diligence to avoid protocol deviations. If an investigator feels a protocol deviation would improve the conduct of the study this must be considered a protocol amendment, and unless such an amendment is agreed upon by Novartis and approved by the IRB/IEC and Health Authorities, where required, it cannot be implemented.

16.1 Appendix 1 List of concomitant medications for patients on asciminib

In general, the use of any concomitant medication deemed necessary for the care of the patient is permitted in this study, except as specifically prohibited in [Section 6.2](#) for patients.

The following lists are based on the internal [Pharmacokinetic Sciences memorandum on Drug-Drug Interaction] (release date: January 2018), which was compiled from the Indiana University School of Medicine’s “Clinically Relevant” Table and supplemented with the FDA Draft Guidance for Industry, Drug Interaction Studies – Study Design, Data Analysis, and Implications for Dosing and Labeling (2017), and the University of Washington’s Drug Interaction Database (2017). These lists are not comprehensive and are only meant to be used as a guide. Please contact the medical monitor with any questions. **If a medication appears on both the list of prohibited and the list of medications to be used with caution, the medication is prohibited.**

Table 16-1 Prohibited concomitant medications for asciminib

| Category | Drug Names |
|--|---|
| Strong inducers of CYP3A | carbamazepine, enzalutamide, lumacaftor, mitotane, phenobarbital, phenytoin, rifabutin, rifampicin, St. John’s wort (Hypericum perforatum) ³ |
| UGT1A1/2B7 inducers | UGT1A1: carbamazepine, cigarette smoke, rifampicin, testosterone propiate, UGT2B7: Barbiturates |
| Cohort C only : Strong inhibitors of CYP3A | atazanavir/ritonavir ¹ , danoprevir/ritonavir ¹ , darunavir/ritonavir ¹ , elvitegravir/ritonavir ¹ , indinavir/ritonavir ¹ , lopinavir/ritonavir ¹ , saquinavir/ritonavir ¹ , tipranavir/ritonavir ¹ , ombitasvir/paritaprevir/dasabuvir/ritonavir (Viekira Pak) ¹ , boceprevir, clarithromycin, cobicistat, conivaptan, grapefruit juice ² , idelalisib, indinavir, itraconazole, ketoconazole, mibefradil, nefazodone, nelfinavir, posaconazole, ritonavir, telaprevir, telithromycin, troleandomycin, voriconazole |
| Torsade de pointe (TdP) TdP/QT risk : Known | amiodarone, anagrelide, arsenic trioxide, astemizole (off us mkt), azithromycin, bepridil (off us mkt), chloroquine, chlorpromazine, cimetidine, cisapride (off us mkt), citalopram, clarithromycin, cocaine, disopyramide, dofetilide, domperidone (not on us mkt), donepezil, dronedarone, droperidol, erythromycin, escitalopram, flecainide, fluconazole, grepafloxacin (off market worldwide), halofantrine, haloperidol, ibutilide, levofloxacin, levomethadyl (off mkt worldwide), mesoridazine (off mkt worldwide), methadone, moxifloxacin, ondansetron, oxaliplatin, papaverine HCl, pentamidine, pimozide, probucol (off mkt worldwide), procainamide (oral off us mkt), propofol, quinidine, sevoflurane, sotalol, sparfloxacin (off us mkt), sulpiride (not on us mkt), terfenadine (off us mkt), thioridazine, vandetanib |
| TdP/QT risk: Possible | alfuzosin, apomorphine, aripiprazole, artenimol+piperazine, asenapine, bedaquiline, bortezomib, buprenorphine, capecitabine, ceritinib, clomipramine, clozapine, crizotinib, cyamemazine (cyamepromazine) (Only on Non US Market), dabrafenib, dasatinib, degarilix, delamanid (off US mkt), desipramine, dexmedetomidine, dolasetron, eribulin, ezogabine, famotidine, felbamate, fingolimod, foscarnet, gemifloxacin, granisetron, hydrocodone-ER, iloperidone, imipramine (melipramine), isradipine, lapatinib, lenvatinib, leuprolide, lithium, mifepristone, mirabegron, mirtazapine, moexipril/hctz, nicardipine, nilotinib, norfloxacin, nortriptyline, ofloxacin, olanzapine, osimertinib, oxytocin, paliperidone, panabinstat, pasireotide, pazopanib, perflutren lipid microspheres, pipamperone (not on us mkt), promethazine, quetiapine, ranolazine, rilpivirine, risperidone, roxithromycin (on non us mkt), saquinavir, sertindole (on non us mkt), sorafenib, sunitinib, tacrolimus, tamoxifen, telavancin, telithromycin, tetrabenazine (orphan drug in us), tizanidine, tolterodine, toremifene, trimipramine, vardenafil, vemurafenib, venlafaxine, vorinostat, zotepine |

| Category | Drug Names |
|---|---|
| TdP/QT risk: Conditional | amantadine, amisulpride, amitriptyline, atazanavir, chloral hydrate, diphenhydramine, doxepin, fluoxetine, furosemide (frusemide), galantamine, hydrochlorothiazide, hydroxyzine, hydroxychloroquine, indapamide, itraconazole, ivabradine (on non us mkt), ketoconazole, loperamide, metoclopramide, metronidazole, nelfinavir, pantoprazole, paroxetine, posaconazole, quinine sulfate, ritonavir, sertraline, solifenacin, telaprevir, torsemide, trazodone, voriconazole, ziprasidone |
| 
¹ Combination ritonavir-boosted regimens are listed here in the DDI memo as strong CYP3A inhibitors (to avoid potential confusion), even though some are considered moderate CYP3A inhibitors in the UW DDI Database.
 
² The effect of grapefruit juice varies widely among brands and is concentration-, dose-, and preparation-dependent. Studies have shown that it can be classified as a “strong CYP3A inhibitor” when a certain preparation was used (e.g., high dose, double strength) or as a “moderate CYP3A inhibitor” when another preparation was used (e.g., low dose, single strength).
 
³ Herbal product
 | |

Table 16-2 Concomitant medications to be used with caution

| Category | Drug Names |
|--|--|
| Cohorts A and B only: Strong inhibitors of CYP3A | atazanavir/ritonavir ¹ , danoprevir/ritonavir ¹ , darunavir/ritonavir ¹ , elvitegravir/ritonavir ¹ , indinavir/ritonavir ¹ , lopinavir/ritonavir ¹ , saquinavir/ritonavir ¹ , tipranavir/ritonavir ¹ , ombitasvir/paritaprevir/dasabuvir/ritonavir (Viekira Pak) ¹ , boceprevir, clarithromycin, cobicistat, conivaptan, grapefruit juice ² , idelalisib, indinavir, itraconazole, ketoconazole, mibefradil, nefazodone, nelfinavir, posaconazole, ritonavir, telaprevir, telithromycin, troleandomycin, voriconazole |
| Narrow therapeutic index substrates of CYP2C8 | paclitaxel |
| Narrow therapeutic index substrates of CYP2C9 | phenytoin, warfarin |
| Narrow therapeutic index substrates of CYP3A | alfentanil, cyclosporine, dihydroergotamine, ergotamine, fentanyl, sirolimus, terfanadine |
| BCRP Inhibitors | abacavir, amprenavir, atorvastatin, curcumin ³ , cyclosporine ³ , daclatasvir, declatasvir ³ , delavirdine, efavirenz, elbasvir, eltrombopag ³ , elvitegravir ³ , erlotinib, fluvastatin, fostamatinib, fumitremorgin, gefitinib, grazoprevir, lapatinib ³ , ledipasvir ³ , lopinavir, paritaprevir ³ , pitavastatin, rosuvastatin, simvastatin, sulfasalazine, tipranavir ³ , velpatasvir, venetoclax |
| P-gp inhibitors | alogliptin, amiodarone ⁴ , azithromycin ⁴ , canaglifozin, captopril ⁴ , carvedilol ⁴ , clopidrogel, cremophor RH40, curcumin, diltiazem ⁴ , dronedarone ⁴ , elacridar ⁴ , eliglustat, felodipine ⁴ , fluvoxamine ⁴ , fostamatinib, ginko ^{4,5} , isavuconazole, ivacaftor, lopinavir, milk thistle (silymarin, silibinin) ^{4,5} , nifedipine ⁴ , nitredipine ⁴ , ombitasvir, paritaprevir, propafenone, quercetin ⁴ , ritonavir ⁴ , sequinavir ⁴ , schisandra chinesis extract ^{4,5} , simeprevir, St. John's wort extract (Hypericum perforatum) ^{4,5} , suvorexant, talinolol ⁴ , telaprevir ⁴ , telmisartan ⁴ , ticagrelor ⁴ , tipranavir ⁴ , tolvaptan ⁴ , valsopodar, vandetanib, verapamil ⁴ , voclosporin, vorapaxar |
| 
¹ Combination ritonavir-boosted regimens are listed here in the DDI memo as strong CYP3A inhibitors (to avoid potential confusion), even though some are considered moderate CYP3A inhibitors in the UW DDI Database.
 
³ Evidence of in vivo DDI
 
⁴ Dual P-gp and CYP3A4 inhibitor
 
⁵ Herbal product
 | |

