6.2.2 Prohibited medication

Other anticancer agents

The administration of any other anticancer agents including chemotherapy and biologic agents is not permitted except for anti-cancer treatments of newly diagnosed solid cancers (e.g. prostate cancer) that would not impact the level of minimal residual disease of patients. These patients may remain in the current study after consultation with Novartis. The administration of other tyrosine kinase inhibitors indicated for treatment of CML are **not** allowed.

Strong CYP3A inducers

Any strong CYP3A inducers should be discontinued 7 days before the first dose of study medications.

Every effort should be made NOT to concomitantly administer strong CYP3A inducers during the study. If administration of a strong CYP3A inducer cannot be avoided during the study and cannot be switched to an alternative therapy, investigator should exercise caution while patient is on study treatment.

Cohort C only (200 mg BID): Strong CYP3A inhibitors

Any strong CYP3A inhibitors should be discontinued 7 days before the first dose of study medications.

Every effort should be made NOT to concomitantly administer strong CYP3A inhibitors. CYP3A inhibitors may decrease the metabolism of asciminib and resulting in increased plasma concentrations and increased exposure. If administration of a strong CYP3A inhibitor cannot be avoided during the study and cannot be switched to an alternative therapy that does not strongly inhibit CYP3A, asciminib must be interrupted.

A list of cytochrome P450 isoenzymes and CYP3A inhibitors may be found at medicine.iupui.edu/CLINPHARM/ddis/clinical-table.

A classification of CYP3A SmPC can be found in Section 16, [Table 16-2](#).

Further information can also be found in the following reference ([Venkatakrishnan et al 2001](#)).

UGT1A/2B inducers

The use of strong inducers of UGT1A/2B is prohibited during the study.

If administration of UGT1A/2B inducer cannot be avoided during the study and cannot be switched to an alternative therapy, temporary interruption of study treatment is NOT needed.

QT prolonging agents

As far as possible avoid co-administering drugs with a “Known”, “Possible” or “Conditional” risk of Torsades de Pointes (per www.crediblemeds.org/) during the course of the study:

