- If concomitant administration of drugs with a “Known risk of Torsades de Pointes” is required and cannot be avoided, study drug must be interrupted. If, based on the investigator assessment and clinical need, study treatment is resumed, close ECG monitoring is advised.
- If during the course of the study, concomitant administration of a drug with “Possible risk” or “Conditional risk of Torsades de Pointes” is required, based on the investigator assessment and clinical need, study treatment may be continued under close ECG monitoring to ensure patient safety.

A list of drugs associated with QT prolongation and/or Torsades de Pointes is available online at www.crediblemeds.org/.

Herbal medications

Herbal preparations/medications are not allowed throughout the study. These herbal medications include, but are not limited to: St. John’s wort, Kava, ephedra (ma huang), ginkgo biloba, dehydroepiandrosterone (DHEA), yohimbe, saw palmetto, and ginseng. Patients should stop using these herbal medications 7 days prior to first dose of study drug.

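### Protocol 6.2.1 allows every acid reducer although cimetidine is listed as Known torsades risk, and Table 16-1 labels Possible- and Conditional-risk drugs prohibited without pointing to the 6.2.2 rule that lets treatment continue

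*Protocol*

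**What the plan says.** **Acid reducers.** Protocol Section 6.2.1, under the sub-heading on gastric pH, states that drugs raising gastric pH do not affect asciminib absorption and then permits the whole class. It mentions no QT exception.

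**QT-prolonging drugs in the text.** Section 6.2.2 opens its QT rule with "As far as possible avoid co-administering drugs with a" Known, Possible or Conditional TdP risk, and then separates the tiers:

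- Known risk: if the drug "is required and cannot be avoided, study drug must be interrupted". If the investigator later judges that "study treatment is resumed, close ECG monitoring is advised".
- Possible or Conditional risk: if the drug is required, "study treatment may be continued under close ECG monitoring to ensure patient safety".

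**QT-prolonging drugs in the appendix.** Table 16-1, titled "Prohibited concomitant medications for asciminib", has separate rows for Known, Possible and Conditional risk that apply to all cohorts. The Conditional row includes "diphenhydramine, doxepin, fluoxetine, furosemide (frusemide), galantamine, hydrochlorothiazide, hydroxyzine, hydroxychloroquine, indapamide". None of the three rows refers to the 6.2.2 contingencies.

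**Other bars in 6.2.2.** "The administration of any other anticancer agents including chemotherapy and biologic agents is not permitted except for anti-cancer treatments of newly diagnosed solid cancers", and "The administration of other tyrosine kinase inhibitors indicated for treatment of CML are" not allowed. In Cohort C, an unavoidable strong CYP3A inhibitor requires asciminib to be interrupted.

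**Tie-break.** Section 6.2.1.1 and Appendix 1 both say that a drug on both the prohibited and the caution list counts as prohibited (the both-lists rule below).

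**Anti-emetics.** Section 6.2.4 says that some carry a Known TdP risk and are prohibited. It refers the reader to 6.2.1.1 and Appendix 1.

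**The concern.** A site has three places to look, and they do not give the same answer. A site relying on 6.2.1 could give cimetidine and keep asciminib running, although 6.2.2 calls for interruption. A site relying on the title of Table 16-1 could refuse a drug that 6.2.2 allows under ECG monitoring. The second case arises from the protocol's own toxicity guidance: a footnote to Table 6-2 recommends antidiarrheal medication at the first sign of loose stools, and loperamide is in the Conditional row.

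The label also has consequences. Section 9.1.1 makes use of prohibited treatment a permitted, though not mandatory, ground for stopping study treatment and refers to the appendices. Section 12.4 makes notable ECG abnormalities a variable of the primary safety analysis, so QT-risk co-medication should be handled in the same way at every site.

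**Working it through.** No arithmetic decides this point; the passages are set side by side.

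**1. Acid reducers**

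| Drug | Row in Table 16-1 | Section 6.2.1 | Section 6.2.2, if required | In Table 16-2? |
|---|---|---|---|---|
| Cimetidine | Known | Allowed | Interrupt asciminib; may resume with ECG monitoring | No |
| Famotidine | Possible | Allowed | May continue under ECG monitoring | No |
| Pantoprazole | Conditional | Allowed | May continue under ECG monitoring | No |

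Two routes might settle the cimetidine conflict. The both-lists rule does not apply, because cimetidine is not in Table 16-2. Appendix 1 defers to Section 6.2, but 6.2.1 and 6.2.2 are both part of Section 6.2, so deferring does not choose between them.

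**2. Possible and Conditional rows**

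The rows hold 79 and 33 entries, 79 + 33 = 112 drug names. The nine drugs in the Conditional-row quotation show the mismatch cleanly. None is in Table 16-2, none is in the strong CYP3A inhibitor row, and none is an anticancer agent. Under 6.2.2 study treatment may continue with any of them if required, while the table title says prohibited.

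The mismatch does not extend to every name in the two rows:

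- Dasatinib and nilotinib are barred as other CML tyrosine kinase inhibitors.
- Other anticancer agents are barred, apart from the exception for newly diagnosed solid cancers.
- In Cohort C, strong CYP3A inhibitors require interruption.
- In Cohorts A and B, Table 16-2 has 27 entries in its strong CYP3A inhibitor row. Eight of them, matched by exact name, are also in the Possible or Conditional rows: telithromycin, itraconazole, ketoconazole, nelfinavir, posaconazole, ritonavir, telaprevir and voriconazole. The both-lists rule makes these prohibited.

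**3. Which reading was intended**

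Exclusion criterion 3 names only Known-risk drugs that cannot be stopped or replaced 7 days before dosing. Section 6.2.4 likewise calls only Known-risk anti-emetics prohibited. Both fit the tiered rule in 6.2.2 better than a uniform ban.

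**4. Cross-reference in 6.2.4**

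Section 6.2.1.1 deals with CYP substrates and inhibitors, BCRP and P-gp. It contains nothing on TdP; the QT text is in 6.2.2.

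**The case against.** The best defence is that the protocol uses the word prohibited loosely throughout. Section 6.2.2 is itself headed as prohibited medication, yet it gives contingencies for several classes. Strong inducers of UGT1A/2B, for example, are prohibited, but if one is unavoidable asciminib need not be interrupted. On this view the table names the drugs and 6.2.2 says what to do when one is needed. Appendix 1 supports that: it refers to Section 6.2 for what is prohibited, calls its lists a guide, and names the medical monitor for questions. This largely stands, and it makes the row-label point weaker than the cimetidine point. A pointer on the rows is still needed, because reaching this reading means inferring against the table's title.

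On cimetidine, the permission in 6.2.1 follows an absorption argument and can be read as clearing only the pH interaction. In addition, the 6.2.2 trigger is the external TdP classification that it cites, whereas Table 16-1 derives from an internal memorandum of January 2018. Whether the external source also rates cimetidine as Known cannot be checked from the documents. Both remarks are fair, but the sentence in 6.2.1 carries no such limit, and the protocol's own table says Known.

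A reader might also infer that the both-lists rule wrongly turns caution into prohibition for itraconazole, voriconazole and the like in Cohorts A and B, and should be switched off for these rows. The documents do not support that. The rule is stated twice, foresees the overlap, and covers drugs that may raise asciminib exposure and also carry TdP risk. Relaxing it would loosen a safety restriction.

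**Conclusion.** The inconsistency holds and is minor to moderate. The acid-reducer conflict is the sharper part: 6.2.1 permits without limit a drug that Table 16-1 places in the tier for which 6.2.2 requires interruption, and no rule in the protocol resolves it. The missing pointer on the Possible and Conditional rows and the wrong reference in 6.2.4 are smaller, but real.

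Two stronger conclusions would go too far. One is that all 112 names in the two rows are wrongly prohibited. Some are barred on other grounds, and a count of drug names says nothing about how many patients are affected; the documents give no figure for patients on these drugs. The other is that the trial's results or its patients' safety are materially compromised. The safety analysis is descriptive, no sample size or error rate is involved, and centrally read triplicate ECGs (Section 8.3.2.1) and the QTcF action rules (Section 6.5.2.1) apply regardless of co-medication.

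The conclusion assumes, from general pharmacology, that cimetidine, famotidine and pantoprazole are acid reducers, that loperamide is an antidiarrheal, and that none of the nine drugs quoted from the Conditional row is an anticancer agent. It takes the risk tiers as printed in Table 16-1.

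**What to change.** 1. **Section 6.2.1:** say that acid reducers are permitted as far as gastric pH is concerned, and that those with TdP risk follow the QT rules in 6.2.2 (for example cimetidine, Known; famotidine, Possible; pantoprazole, Conditional).
2. **Table 16-1, Possible and Conditional rows:** add the label *avoid if possible; if required, see 6.2.2 (close ECG monitoring), unless barred by another 6.2.2 rule or by the both-lists rule*.
3. **Section 6.2.4:** replace the reference to 6.2.1.1 with 6.2.2.

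Leave the both-lists rule and the Table 16-2 entries as they are, so that strong CYP3A inhibitors that also carry TdP risk stay prohibited in Cohorts A and B.

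The cost is protocol wording and a memo to sites. No procedure, sample size or analysis changes.
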